### **12.5.5 Overdose**

The Investigator must immediately notify the Sponsor of any occurrence of overdose with study drug.

### **12.6 ECOG Performance Status**

ECOG performance status will be evaluated at the visits indicated in the Schedule of Assessments ([Table 9-1](#)). A summary of ECOG performance status is provided in Table 12-4.

**Table 12-4 ECOG Performance Status**

Grade	Description
0	Fully active, able to carry on all pre-disease performance without restriction
1	Restricted in physically strenuous activity but ambulatory and able to carry out work of a light or sedentary nature, e.g., light house work, office work
2	Ambulatory and capable of all self-care but unable to carry out any work activities. Up and about more than 50% of waking hours
3	Capable of only limited self-care, confined to bed or chair more than 50% of waking hours
4	Completely disabled. Cannot carry on any self-care. Totally confined to bed or chair
5	Dead

### **12.7 Immunogenicity**

Safety assessment will also include evaluation of immunogenicity (i.e., ADAs). Immunogenicity assessments will be performed on Day 1 of Cycles 1-8, Cycle 12 and every 4 cycles thereafter, as well as end of study or early termination visit ([Table 9-1](#)).

If a patient is found to be ADA-positive at the end-of-study, the persistence of the ADA will be evaluated by collecting one more sample, 4 months later after the last study visit. The serum from each time point will test for anti-OBI-999 antibody concentration by a validated assay.

## 13 Exploratory Analyses

### 13.1 Tumor Tissue Samples

Tumor tissue biopsy or tissue samples will be collected at time of screening in both Part A and Part B of the study. Fresh (preferred) or archival tissue that is less than 10 years old is acceptable. Tumor tissue samples with fewer than 100 tumor cells will be deemed not evaluable. A fine needle aspirate, frozen sample, plastic embedded sample, bone, bone marrow, cell block, clot, cytologic specimen, decalcified sample, or formalin fixed sample that was frozen at any point prior to fixation will not be accepted. All attempts should be made to obtain fresh biopsy specimens. However, if historical sample is available, they should be retained along with histology/pathology report, if possible. All fresh biopsy specimens or historical samples should be sent to the qualified laboratory for testing. A minimum of 5 slides are required for the central laboratory Globo H assay for determination of eligibility for Part B. Up to 10 unstained additional slides should be provided, depending on availability, for testing tumor associated biomarkers as well as conducting a bridging study for the future companion diagnostic test.

The mandated baseline slides are to be used for Globo H testing by IHC to define the level and extent of Globo H expression, as this is the target of OBI-999. The 5 slides required for patients in Part B are part of the eligibility assessments, as all patients in Part B of the study must have a Globo H H-score of  $\geq 100$  to be eligible for study entry.

An analysis will be performed to determine whether there is a potential correlation between baseline tumor Globo H expression as assessed by IHC H-score and response to OBI-999 treatment, as assessed by change from baseline in the sum of diameters of measurable lesions and by RECIST response.

Apart from the mandatory Globo H assessments, up to 10 additional slides have been requested, if available, to identify potential predictive biomarkers for OBI-999 activity such as assessment of expression of additional tumor-associated glycans which may be pathologically associated with Globo H overexpression (e.g., SSEA-3 and SSEA-4) or molecular phenotypes of tumors which may be associated with aberrant Globo H expression.

## 14 Statistical Analysis

The Statistical Analysis Plan (SAP) will be prepared after the protocol is approved. This document will provide further details on the definitions of analysis populations, variables, and methodology in order to address all study objectives. The SAP will serve as a complement to the protocol and supersedes it in case of differences.

The statistical evaluation will be performed using the SAS® Version 9.4 or higher (SAS Institute, Cary, NC).

Analyses will be conducted by dose level in Part A and by cancer type in Part B. Descriptive summaries for categorical variables will include counts and percentages. Descriptive

summaries for continuous variables will include means, medians, standard deviations, minimum, and maximum values. Categorical ordinal variables will be presented as a combination of class frequencies and percentages, together with mean and standard deviations of the ordinal scores. Descriptive summaries of time to event data will include medians and confidence intervals. Graphical summaries of the data may be presented. All data will be listed for all patients.

Further details of the analysis, including the handling of missing data, transformations, other data handling procedures, and analytical methodology will be provided in the SAP. Additional exploratory analyses of the data will be conducted as deemed appropriate.

### **14.1 Determination of Sample Size**

This is a 2-part study: Part A (Dose-Escalation) and Part B (Cohort-Expansion).

Up to 30 patients were to have been enrolled in the 3+3 dose-escalation portion of the study (Part A).

The cohort-expansion portion of the study (Part B) will enroll up to 57 patients based on Simon's two-stage design. The first stage will recruit up to 9 patients in each of three cohorts. If at least 1 objective response is observed, a second stage recruitment will occur with up to 10 additional patients enrolled into that cohort, for a total of up to 19 patients per cohort. If at least 4 objective responses are observed in the 19 patients, then OBI-999 will be considered worthy of further evaluation in that indication. Patients will be followed up to the 24-week scheduled response assessment for the purposes of counting objective responses for Simon's two-stage design success criteria. This design is based on a level of low interest for a treatment with an ORR of 10% versus a level of high interest for a treatment with an ORR of 25%. The sample size is based on a one-sided alpha of 0.12 and 72% power. The two-stage design limits the number of patients treated for a treatment with low levels of activity.

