	
 
• Days 2, 4, 8, 11 and 15 of Cycles 1 and 2 (ie, 24, 72, 168, 240 and 336 hours after the end of infusion).
 
• Day 1 of Cycle 3 and Cycle 4 – prior to infusion and 30 minutes after the end of infusion.
 
• Day 8 of Cycle 3 and Cycle 4 – 168 hours after the end of infusion.
 
• Day 1 of Cycles 5-8, 12 and every 4 cycles – prior to infusion and 30 minutes after the end of infusion.
 
• End of treatment visit – single sample.
 
 
Part B of the study:
 
 
• Day 1 of Cycles 1 and 2 – prior to infusion, and 30 minutes and 6 hours after the end of infusion.
 
• Days 2 and 4 of Cycles 1 and 2 (ie, 24 and 72 hours after the end of infusion, this intensive PK sampling will be collected from first 5 patients in each cohort).
 
• Day 8 and 15 of Cycles 1 and 2 (ie, 168 and 336 hours after the end of infusion).
 
• Day 1 of Cycle 3, Cycle 4, Cycle 8, and every 4 cycles - prior to infusion and 30 minutes after the end of infusion.
 
• End of treatment visit – single sample.
 
 
Pharmacokinetic parameters will be calculated using a non-compartmental method from the PK samples collected during Cycles 1 and 2 and will include but will not be limited to maximum serum concentration (<math>C_{max}</math>), area under the concentration curve (AUC), elimination half-life (<math>t_{1/2}</math>), clearance (Cl), time to reach maximum concentration (<math>T_{max}</math>), and volume of distribution (<math>V_d</math>).
 
Preliminary Clinical Activity Profile:
 
Tumor response will be evaluated by the Investigator using RECIST 1.1. Tumor status assessment will be performed pretreatment (up to 28 days prior to dosing). During the study, tumor response will be assessed every 6 weeks for the first 3 months and then every 9 weeks until discontinuation of study treatment, disease progression, death, or initiation of further systemic cancer therapy, including radiation therapy, whichever occurs earlier.

Study Endpoints:	
Part A – Dose-Escalation:
 
Primary endpoints:
 
 
• AEs/SAEs and laboratory abnormalities as graded by NCI CTCAE version 5.0.
 
• DLTs with OBI-999.
 
• MTD and RP2D of OBI-999.
 

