**Table 9-1 Schedule of Assessments**

Study Procedure	Screening Visit	Treatment Period						EoS / ET	F/U
		Cycle 1					Cycle 2-35		
Cycle (C) #	-								
Cycle # and Day		C1D1	C1D2	C1D4	C1D8	C1D11	C1D15	D1	
Window period (days)	-28 to -1	-1*	±1	±3	±3	±3	±3	±3	±7
Informed consent a	X								
Demographics	X								
Eligibility screening	X	X							
Medical history b	X	X							
Physical examination c	X	X			X*		X	X	X
Height, weight d	X d	X					X	X	
Vital signs e	X	X					X	X	
Ophthalmology examination f	X						Q6wk for the first 6 months, then Q9wk thereafter f		X
ECOG g	X						X	X	
12-lead ECG h	X	X		X g				X	
Pregnancy testing i	X							X	
Tumor biopsy j	X								
Hematology and serum chemistry k	X	X			X		X	Every week for Cycles 2 and 3, then D1 of Cycles 4+	X
Coagulation and urinalysis l	X							D1 of each 21-day cycle l	X
Drug administration m		X						D1 of each 21-day cycle	
Pharmacokinetic sample n			See footnote n						
Immunogenicity (ADA) o		X						See footnote o	X
Radiology evaluations (CT or MRI) p	X							Q6wk for the first 3 months, then Q9wk thereafter	X
Concomitant medications		↔							
Adverse events		↔							→

Abbreviations: ADA = anti-drug antibody; D = Day; C = Cycle; CT = computed tomography; ECG = electrocardiogram; ECOG = Eastern Cooperative Oncology Group; EoS = End of Study; ET = Early Termination; F/U = follow-up; MRI = magnetic resonance imaging; Q6wk = every 6 weeks; Q9wk = every 9 weeks

EoS Visit is the safety follow-up visit, conducted  $28\pm 7$  days after the last OBI-999 dose. ET Visit lab assessments will be conducted for patients discontinuing study treatment, if last available tests are before 2 weeks.

\*The - 1 day window (1 day prior) for C1D1 is for safety laboratory assessments. Blood can be drawn 1 day prior to initiation of study drug infusion on C1D1. Safety laboratory results should be available and reviewed by the Investigator prior to the OBI-999 administration.

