p. Radiology (CT or MRI scan) evaluations of tumor response: Performed during screening and during the study every 6 weeks for the first 3 months, and then every 9 weeks until discontinuation of study treatment, disease progression, death, or initiation of further systemic cancer therapy, including radiation therapy, whichever occurs earlier. CT or MRI scan will be performed within 1 week prior to the start of the next cycle. Unscheduled scan can be performed anytime, if needed to confirm disease progression. Radiology assessment for early termination/end of study, should ONLY be performed if  $\geq 9$  weeks have passed from the previous scheduled CT/MRI scan. Same assessment method and same technique should be used on each patient while on study.

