## **10 Clinical Activity Profile Assessments**

Radiology (CT or MRI scan) evaluations ( $\pm 7$  days) of tumor response are to be performed during screening within 28 days prior to Cycle 1 Day 1 (first dose of study medication), and thereafter during the study every 6 weeks for the first 3 months and then every 9 weeks until discontinuation of study treatment, disease progression, death, or initiation of further systemic cancer therapy, including radiation therapy. Radiology assessment for end of study follow-up and early termination should be performed unless the patient already has radiographic confirmation of progressive disease  $\leq 9$  weeks prior to permanent discontinuation of study drug. The same assessment method and the same technique should be used on each patient while on study.

An end-of-treatment radiology assessment should be performed unless the patient already has radiographic confirmation of progressive disease  $\leq 9$  weeks prior to permanent discontinuation of study drug. The same assessment method and the same technique should be used on each patient while on study.

Overall tumor response and progression will be evaluated by the Investigator according to RECIST 1.1.

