5.4 INTERIM ANALYSIS

There will not be any other formal interim analyses except for the one related to Simon's two stage design described below; however, a description of the Dose-Escalation Phase and the selection of the RP2D may be written up for the purposes of a manuscript.

Moreover, the cohort expansion portion of the study (Part B) will enrol up to 57 patients based on Simon's two-stage design. The first stage will recruit up to 9 patients in each of three cohorts. If at least one objective response is observed, a second stage recruitment will occur with up to 10 additional patients enrolled into that cohort, for a total of up to 19 patients per cohort. If at least 4 objective responses are observed in the 19 patients, then OBI-999 will be considered worthy of further evaluation in that indication. Patients will be followed up to the 24-week scheduled response assessment for the purposes of counting objective responses for Simon's two-stage design success criteria. A formal analysis will be performed to support it.

Patient enrolment, patient disposition, baseline characteristics, cancer history, clinical benefit rate, exposure to OBI-999, AE and ECG summaries (all described in this document) will support this formal analysis at end of stage 1.

If Simon's two-stage design success criteria is not met, then the second stage recruitment will not occur, and analyses will be done for supporting an aCSR.

The description above represents the initial interim analysis planning based on the protocol. In reality at the end of the first stage of Part B, four patients did not have a RECIST post-baseline assessment and so it has been decided to replace them to have enough data to perform the go/no-go analysis. 2 'replacement' patients have been enrolled in the pancreatic cohort, while searching for 2 'replacement' patients in the colorectal cohort was in progress. On 10th November 2023, Sponsor stated they stop the study and elected to generate an aCSR and so formal go/no-go analysis never happened.

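### Does closing the Simon response count at week 24, where no scan is scheduled, leave the go/no-go rule undefined?

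*Protocol*

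**What the plan says.** The Simon rule is in Protocol 14.1 and SAP 7: nine patients per cohort in stage 1, ten more if at least one responds, and success at four or more responses in 19. The design contrasts an ORR of 10% with one of 25%, at one-sided alpha 0.12 and 72% power. The closing point for counting is: "Patients will be followed up to the 24-week scheduled response assessment for the purposes of counting objective responses". The same sentence stands in the Protocol Synopsis (Planned Sample Size), Protocol 6.1.3, and SAP 5.1.4, 5.4 and 7.

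The imaging schedule is the same wherever it is given. The Synopsis says "tumor response will be assessed every 6 weeks for the first 3 months and then every 9 weeks until discontinuation of study treatment". Table 9-1 has "Q6wk for the first 3 months, then Q9wk thereafter", and the schedule in SAP Appendix I agrees. Protocol 10 adds a ±7 day window. Footnote p of Table 9-1 ties scans to the 21-day cycle: "CT or MRI scan will be performed within 1 week prior to the start of the next cycle".

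Protocol 14.3 and SAP 10.7.1 define ORR as confirmed CR or PR, seen at two or more consecutive assessments at least 3 weeks apart.

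On the present status of the rule, SAP 5.4 says: "The description above represents the initial interim analysis planning based on the protocol". It then reports for 10 November 2023: "Sponsor stated they stop the study and elected to generate an aCSR and so formal go/no-go analysis never happened".

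**The concern.** A decision rule needs a closing point that exists. Here the text names a scheduled assessment at week 24, and the schedule has none. One analyst could close the count at the last scan before week 24 and another at the first scan after it. The thresholds turn on single patients, 0 versus 1 of 9 and 3 versus 4 of 19, so one late responder treated differently could reverse a cohort's decision. The SAP, which takes precedence over the protocol where they differ, repeats both statements without reconciling them.

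**Working it through.** **1. The plan's own figures.** Inputs from Protocol 14.1: n1 = 9, n2 = 10, continue if X1 ≥ 1, success if X1 + X2 ≥ 4. The success probability at response rate p is the sum over x = 1 to 9 of P(X1 = x) × P(X2 ≥ 4 − x).

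- At p = 0.25: x = 1 gives 0.2253 × 0.4744 = 0.1069; x = 2 gives 0.3003 × 0.7560 = 0.2270; x = 3 gives 0.2336 × 0.9437 = 0.2204; x ≥ 4 gives 0.1657. The total is 0.720, which matches the stated 72%.
- At p = 0.10: 0.0272 + 0.0454 + 0.0291 + 0.0083 = 0.110, below the stated 0.12.

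**2. The scan weeks.** The documents do not say where the 9-week interval starts, so three starts were tried.

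| Start of 9-week interval | Scans (weeks) | Windows nearest week 24 (±1 week) | Reaches week 24? |
|---|---|---|---|
| Week 12 | 6, 12, 21, 30 | 20–22, 29–31 | No |
| Week 13 | 6, 12, 22, 31 | 21–23, 30–32 | No |
| Multiples of 9 from baseline | 6, 12, 18, 27 | 17–19, 26–28 | No |

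The first row fits best with scans tied to the 21-day cycle, since 6, 12, 21 and 30 are all multiples of 3. The mismatch is confirmed under every start.

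**3. Who is affected.** Protocol 14.1 states its hypotheses as ORR, and 14.3 defines ORR as confirmed response. On the first-row schedule:

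- First response at week 6: confirmed at week 12. Counts under either reading.
- First response at week 12: confirmed at week 21. Counts under either reading.
- First response at week 21: next scheduled scan at week 30. Counts only if the closing point is the later scan, or if an unscheduled scan confirms it at week 21 + 3 = 24 or sooner after the 3-week minimum. Protocol 9.2 permits unscheduled assessments but does not require one.

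For a patient who stops treatment, footnote p gives little help: "Radiology assessment for early termination/end of study, should ONLY be performed if" at least 9 weeks have passed since the previous scheduled scan.

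**4. How much it could matter.** The documents give no timing of response, so this is an illustration only. Suppose 25% is the rate under the later reading and a share f of those responders is lost under the earlier one, so p = 0.25 × (1 − f). Stage-1 pass is 1 − (1 − p)^9; success is as in step 1.

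| f | p | Stage-1 pass | Success |
|---|---|---|---|
| 0 | 0.2500 | 0.925 | 0.720 |
| 5% | 0.2375 | 0.913 | 0.677 |
| 10% | 0.2250 | 0.899 | 0.631 |
| 20% | 0.2000 | 0.866 | 0.529 |

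Every patient counted under the earlier reading is also counted under the later one. The differences from the first row are therefore the chances that the two readings disagree: 0.012, 0.026 and 0.059 at stage 1, and 0.043, 0.089 and 0.191 at the end. With p = 0.10 × (1 − f), success is 0.110, 0.095, 0.081 and 0.057, so type I error never exceeds 0.110.

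**The case for a change.** The best case for a change is that the rule was left uncorrected in SAP Final 2.0. Sections 5.1.4 and 7 carry it without the planning-only label that 5.4 gives. The illustration also shows that disagreement need not be trivial if many responses come late. In addition, the abbreviated report gives ORR in the safety population from best overall response, which runs to progression, recurrence or end of study with no 24-week limit (SAP 10.7.1 and 11). A reader could set that ORR against 1 of 9 or 4 of 19, although it is not the Simon count.

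What stands is that the wording is loose. The rest is weaker.

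- The shares f have no basis in the documents, so 0.191 is not an estimate.
- The two readings are not equally natural. Follow-up *up to* week 24 does not ordinarily extend to a scan six weeks later. The last scan at or before week 24 is the sense an analyst would take.
- One could argue that confirmation does not apply to the Simon count, because 14.1 speaks only of responses observed. Its hypotheses are ORRs, however, so confirmation is strongly implied.
- The 24-week limit was written for the Simon count alone. The ORR endpoint never carried it, so an ORR without that limit is what the protocol defined, and neither document plans to compare the two.

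**Conclusion.** The schedule has no week-24 scan, and the closing sentence is a slip of wording. It calls for no change. Analysts would close the count at the last scan at or before week 24, about week 21. The doubt is then confined to a response first seen at that scan.

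Neither reading makes the stated design wrong. Power is 0.720 if 25% is understood as the rate countable within the window, and type I error is at most 0.110 either way. Sample size, thresholds and scan schedule would be the same under both.

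The go/no-go analysis was never done and the study is stopped, so rewording would change no decision and no reported result. This conclusion assumes that confirmation applies to the Simon count, and that the abbreviated report presents ORR as the endpoint it is, without a verdict against the Simon thresholds. If the design were reused in another trial, naming the closing scan would be sensible drafting.

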### **14.2 Analysis of Populations**

The safety population to be analyzed will include all enrolled patients who receive at least 1 dose of study drug. The population used for analysis of clinical activity will be all enrolled patients who received at least one dose of study drug and had at least one follow-up tumor assessment scan.

### **14.3 Clinical Activity Analysis**

ORR is defined as the percentage of patients with confirmed partial response (PR) or complete response (CR) based on tumor assessment as determined by RECIST 1.1. A confirmed response will be defined as two or more consecutive assessments separated by at least 3 weeks. Patients who discontinue due to toxicity or clinical progression prior to post-baseline tumor assessments will be considered as non-responders and retained in the denominator.

CBR is defined as the percentage of patients with confirmed CR, PR, or stable disease. A confirmed response will be defined as two or more consecutive assessments separated by at least 3 weeks. Patients who discontinue prior to post-baseline tumor assessments will be considered as non-responders and retained in the denominator.

DOOR is defined as time from date of reported confirmed PR or CR to the date of progression, and will be summarized descriptively using time-oriented summary statistics. Additionally, a listing of DOOR for those patients experiencing response will be provided.

PFS is defined as the time from first dose of study drug until radiographically determined disease progression or death due to any cause, whichever occurs first. Patients who are still alive or who have no progressive disease reported at analysis, will be censored at their last evaluable tumor assessment.

Kaplan Meier estimates and 95% confidence intervals will be presented for time-to-event endpoints such as PFS, if sufficient numbers of events to calculate meaningful statistics are observed.

#### **14.4 Pharmacokinetic Analysis**

Pharmacokinetic parameters will be calculated using a non-compartmental method from the PK samples collected during Cycles 1 and 2 and will include, but is not limited to  $C_{max}$ , AUC,  $t_{1/2}$ , Cl,  $T_{max}$ , and  $V_d$ .

To describe the dependency on dose, scatter plots of  $C_{max}$  and AUC versus dose will be provided. Summary statistics will be tabulated for the trough concentration ( $C_{min}$ ) and peak concentrations (end of infusion) by dose and study day.

Pharmacometric methods may also be applied to further investigate OBI-999 and MMAE exposure (e.g., accumulation of OBI-999, presence of dose- or time-dependent OBI-999 PK behavior, verification of influential factors on OBI-999 PK).

